At least 50% (18 out of 35) of the scheduled sessions must be completed for each task in order for a given measurement burst to be considered valid. These 35 scores may take longer than 7 days to accumulate but must be taken without 2-week or larger gap between sessions to be included in the analysis. Each burst has a recorded burst start date; sessions recorded prior to this start date are considered part of the pre-burst training and will be discarded. The first day of the Burst 2 measurement should be inside the visit window (i.e., at least one session no earlier than 3 months and no later than 6 months than the 9-month randomization anniversary) for the Burst 2 measurement to be valid and included in the primary analysis. The domain Z-score is computed using the mean and SD for an individual session, estimated from the baseline (Burst 1) distribution and the measurement burst for an individual i at Burst j is the average task scores across the multiple sessions (up to 35) within that burst. The domain Z-score with fewer than 18 valid sessions will be treated as missing and multiply imputed for the primary analysis, which will be an intent-to-treat analysis. The details are as follows.

The mean and SD are calculated for each domain separately from the baseline measurement (Burst 1). For a given domain, let Y_{i1j}^d be the Burst 1 outcome score from domain d , $d=1,2,3$;

person i , $i=1, \dots, n$; and session $k=1, \dots, m_{i1}$, where m_{i1} is the number of successfully completed sessions at baseline for person i (which may vary by domain d), then:

$$\mu^d = \sum_i \bar{Y}_{i1}^d / n; \bar{Y}_{i1}^d = \sum_j (Y_{i1k}^d) / m_{i1}; SD^d = \sqrt{(\sum_i (\bar{Y}_{i1}^d - \bar{Y}_{1.})^2 / (n-1))}.$$

Then for a given measurement burst $j=1, 2, 3, 4$: where $j=1$ represents baseline and $j=2-4$ represents months 9, 18, and 27, respectively; the domain Z-score for subject i and Burst j is denoted by Z_{ij}^d is calculated from Y_{ijk}^d as:

$$Z_{ij}^d = (Y_{ijk}^d - \mu^d) / SD^d.$$

The three primary tasks (variable names) are:

- Z^1 =Symbol search (SYMBOL_SEARCH.median.RT.accurate_trials)
- Z^2 = Grid Memory (DOT_MEMORY.sum.error.distance.overall)
- o Z^3 = Color Shapes (COLOR_SHAPES.CorRec.rate)

The global assessment score for person i at Burst j is calculated as the average of the three domain average Z score, with Z^1 and Z^2 multiplied by negative 1 so increase is improvement:

$$Z_{ij} = (-Z_{ij}^1 - Z_{ij}^2 + Z_{ij}^3) / 3.$$

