The primary analysis will be a between-arm comparison of the change from baseline in global composite cognition score, measured at Burst 2 (approximately month 9) as estimated from the ANCOVA regression model, which also includes adjustment for the stratification factors $Strat_i$ = (sex, age, years of education):

$$Z_{i2} = \beta_0 + \beta_1 Z_{i1} + \beta_2 Arm_i + \beta_3^T Strat_i + e_i.$$

In this model, age and years of education are treated as continuous. The stratification variables are added to assure proper confidence interval width, since randomization included stratification involving these variables (Kahan and Morris 2011). The coefficient β_2 quantifies the difference between treatment arms at Burst 2, adjusted for the baseline Burst 1 composite score measure and stratification variables, and will be fit using linear regression.

A supportive analysis of the primary endpoint will be the adjusted analysis examining the treatment effect on the change from baseline at Burst 2 for each of the three individual task domain scores \bar{Y}_{i2}^d .

Analysis of Secondary Outcomes

We will consider the treatment effect on the individual tasks (symbol search, color shapes and grid memory) in a longitudinal session-level model with the post-baseline session level outcome Y_{ijk}^d ($j>1$) regressed on the baseline average $Y_{i1.}^d$, treatment arm, time since baseline $time_{ij}$, time of day t_{ijk} (continuous covariate 0-24, centered at group average), day of week (i.e work day or day off), season (4 level factor variable: winter, spring, summer, fall), practice effects $g(s_{ijk})$ as a function of s_{ijk} (session number 1-35 as a continuous covariate), and, fatigue (visual

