analogue). A b-spline with 3 degrees of freedom will be used to model a non-linear practice effect and the likelihood ratio test will be used to assess whether non-linear terms for the practice effect are needed. Splines will also be used to fit a circadian rhythm curve for the effect of the time of day of the session $f(t_{ijk})$. For the continuous tasks (grid memory and symbol search), linear mixed effects model will be fit with a random intercept to account for the correlation of repeated measures within an individual (Model 1). Random intercept variances are allowed to vary by burst. We will also consider whether there is evidence for between person variation in the change over time by including random slope terms for the time effects (Model 2). The treatment effect in Models 1 and 2 will be modeled with a main effect an interaction with the continuous time variable. Thus, the following linear mixed effects models will be fit for each continuous domain:

Model 1: Longitudinal linear mixed effects model for repeated measures across burst and session.

$$Y_{ijk}^d = \beta_0 + \beta_1 Y_{i1}^d + \beta_2 \text{Arm}_i + \beta_3 \text{time}_{ij} + \beta_4 \text{Arm} * \text{time}_{ij} + \sum_l \beta_{5l} f(t_{ijk}) + \beta_6 \text{Day}_{ijk} + \beta_5' \text{Season}_{ij} + \sum_m \beta_{8m} g(s_{ijk}) + \beta_9 \text{Fatigue}_{ijk} + \tilde{\beta}_{10}^T \text{Strat}_i + b_{ij} + e_{ijk},$$

Model 2: Longitudinal linear linear mixed effects model for repeated measures across burst and session, including random effects for both slope and intercept.

$$Y_{ijk}^d = \beta_0 + \beta_1 Y_{i0}^d + \beta_2 \text{Arm}_i + \beta_3 \text{time}_{ij} + \beta_4 \text{Arm} * \text{time}_{ij} + \sum_l \beta_{5l} f(t_{ijk}) + \beta_6 \text{Day}_{ijk} + \beta_7' \text{Season}_{ij} + \sum_m \beta_{8m} g(s_{ijk}) + \beta_9 \text{Fatigue}_{ijk} + \tilde{\beta}_{10}^T \text{Strat}_i + b_3 \text{time}_{ij} + b_4 \text{Arm} * \text{time}_{ij} + b_{ij} + e_{ijk},$$

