where b_{ij} is the person level effect (random intercept term) for participant i and Burst j , and e_{ijk} is the residual error term assumed to be mean 0, independent across time and individuals and approximately normally distributed. In this model, response Y_{ijk}^d is modeled as a function of the overall baseline level and the term β_4 summarizes the potential treatment effect on the change over time. Models will be further adjusted for age, gender, APOE4 allele, race, and ethnicity in supportive analyses. The difference in time and underlying cognitive function within a burst is assumed negligible, thus the time and season variables in these models will be determined by the first day of the Burst.

The Color Shapes task has only 7 possible values, so a similar generalized estimating equation (GEE) approach will be taken using the Poisson mean model and robust sandwich variance for the number of incorrect responses (0-6).

Our secondary outcomes also include between arm comparisons of MHD-related dietary intake based on self-report and biomarker measures of intake at 9 months post baseline. Outcome models of between-arm differences in dietary intakes indicative of the MHD as measured by nutritional biomarkers, and self-report at Burst 2 will be conducted in a similar manner to the models specified above for the primary cognitive outcomes: namely, ANCOVA models that adjust for the baseline level, Arm and stratification factors will be fit. Tocopherols and carotenoids plasma biomarkers will be additionally adjusted for cholesterol variables per Gross et al (2003). Longitudinal models considering ASA24 data across the 4 bursts will be fit using similar mixed effects models, simplified to analyze only the Burst level average for the ASA24 dietary intakes (no repeated measures within a burst). Analyses will generally be complete case

analyses for the dietary variables. Energy adjustment will be considered where appropriate. Sensitivity analyses with additional adjustment variables associated with missing, as well as exploratory analyses that examine potentially differences in intervention effect by gender, race, ethnicity and age, will also be considered.

The plasma biomarkers include: total folate, alpha and gamma tocopherol, carotenoids (alpha carotene, beta carotene, zeaxanthin+lutein, beta cryptoxanthin, and vitamin B12), lycopene, and fatty acid profile. Serum sodium is an additional secondary outcome, indicative of hydration.

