Imputation Models for the Ambulatory Cognitive Scores

For the primary analysis, we will use the multiple imputation chained equation approach (MICE) to impute the necessary missing data to allow an ITT analysis (Azur et al. 2011). Burst measures that had fewer than 18 valid sessions for a given domain average (i.e. for \bar{Y}_{ij}^d for $d=1,2,3$; $j=1,2$) or a Burst 2 measure that started outside the Burst 2 window will be treated as missing and imputed.

A sequence of chained equations for MICE will be considered using: all variables in the primary analysis model (i.e., Arm, gender (0=female, 1=male), age at Burst 1, years of education, Burst 1 composite Z-score, and Burst 2 composite Z-score), run-in average variables for each of the tasks 1-3 in the composite outcome (\bar{Y}_{i0}^d), (averaging first 10 or fewer for each), MOCA score, indicator for in-person vs telephone MOCA, and interaction between these two MOCA variables, domain-specific Zscores based on the average of the available data from up to the first 10 sessions at Burst 1 for each of the three tasks 1-3 in the composite outcome, and the Burst 2 domain-specific Zscores using up to the first 10 sessions for each of the three tasks. Additional models may be considered as sensitivity analyses.

The imputation will be conducted in R using the `mice` package defaults for each variable type (e.g., predictive mean matching for the missing continuous variables (Van Buuren 2018). The number of multiple imputations will be greater than 25 (large enough to be stable, in terms of the intervention effect estimates and p-values).

Missing data approach for the secondary outcomes

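### The printed equation for Model 2 uses the run-in subscript for its baseline covariate, contradicting Model 1 and the SAP's own text; probably a notation slip, but it should be corrected

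*SAP*

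**What the plan says.** Under Analysis of the Primary Outcome, the SAP numbers the bursts 1 to 4. Index 1 "represents baseline and" indices 2 to 4 are months 9, 18 and 27. It defines no burst 0.

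Under Analysis of Secondary Outcomes, each post-baseline session score is "regressed on the baseline average", written there with index 1. The equations follow:

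- Model 1: "\beta_0 + \beta_1 Y_{i1}^d + \beta_2"
- Model 2: "\beta_0 + \beta_1 Y_{i0}^d + \beta_2"

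The only stated purpose of Model 2 is to look for between-person variation in change, by "including random slope terms for the time effects (Model 2"). After both equations, the text says the response "is modeled as a function of the overall baseline level".

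Subscript `i0` appears in one other place, the list of imputation variables under Imputation Models for the Ambulatory Cognitive Scores. There it marks the "run-in average variables for each of the tasks 1-3 in the composite outcome", taken over the first 10 sessions or fewer.

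**The concern.** `Y_i0` in Model 2 is not an undefined symbol that would stop a programmer. It matches a variable that exists in the trial data, so literal code would run without error and adjust for a two-day screening score in place of the week-long Burst 1 average.

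Two things would follow. The covariate would rest on at most 10 sessions, against up to 35 (at least 18 for a valid burst), and would explain less of the outcome. Models 1 and 2 would also differ in a fixed effect as well as in their random effects, so a change in fit or in `β2` between them would have two possible causes.

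Model 2 as printed governs the two continuous secondary tasks, Grid Memory and Symbol Search. It is also the template for the exploratory Shopping List task.

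**Working it through.** **The plan's own figures first.** The documents give no precision figure for Model 2. The nearest is in Protocol section 9.2: 80% power for 0.35 SD with 125 per arm. Assuming two-sided α = 0.05, 0.35 × √(125/2) = 2.767 and Φ(2.767 − 1.960) = 79.0%, which agrees. The absolute differences 0.35 × √(2(1 − r)) are 0.157, 0.192 and 0.350 at r = 0.90, 0.85 and 0.5, matching the stated 0.16, 0.19 and 0.35.

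**Inputs**

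- Reliability of person averages in the earlier smartphone study: 0.97 (Grid Memory) and 0.98 (Symbol Search), from 5 prompts × 14 days = 70 sessions (Protocol 2.2.3). At the reported 80% compliance this is 56.
- Burst-to-burst correlation: about 0.90 (Protocol 9.2).
- Burst 1: up to 35 sessions.
- Run-in: two days (Protocol 6.2.1) with tasks after the wake-up and four signalled surveys (Protocol section 3), so 2 × 5 = 10. Protocol 10.3.3 accepts 9 of 12 assessments. If both bedtime surveys, which carry no tasks, are among the 9, then 7 task sessions remain. I use 7 as the low case.

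**Step 1: reliability (Spearman-Brown).** Single-session reliability is ρ = rel / (70 − 69·rel), and for k sessions it is kρ / (1 + (k − 1)ρ).

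| | Grid Memory | Symbol Search |
|---|---|---|
| ρ | 0.97/3.07 = 0.316 | 0.98/2.38 = 0.412 |
| 10 sessions | 0.822 | 0.875 |
| 35 sessions | 0.942 | 0.961 |

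**Step 2: simple ANCOVA at month 9.** The latent correlation is R = 0.90/rel, that is 0.928 and 0.918. The correlation of a k-session covariate with the month 9 average is R·√(rel_k × rel_35), and the residual variance is 1 − r².

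| | Grid Memory | Symbol Search |
|---|---|---|
| r with Burst 1 average | 0.874 | 0.882 |
| r with run-in average | 0.816 | 0.842 |
| Residual variance ratio | 1.41 | 1.31 |
| SE ratio | 1.19 | 1.15 |

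With 7 run-in sessions the SE ratios are 1.27 and 1.22. With 56 reference sessions they run from 1.13 (Symbol Search, 10 sessions) to 1.25 (Grid Memory, 7 sessions).

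**Step 3: all three follow-up bursts.** Latent variance is 1 at each burst, with correlation R between bursts (exchangeable) or R^(gap/9 months) (autoregressive). Session error (1 − ρ)/ρ is divided by the number of sessions. Let C be the covariance of the three follow-up averages given the baseline covariate. The arm difference is fitted as `β2 + β4 × time`, with covariance proportional to (XᵀC⁻¹X)⁻¹. SE ratios, run-in covariate over Burst 1 covariate, across both tasks and both correlation structures with 70 reference sessions:

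| | 10 run-in sessions | 7 run-in sessions |
|---|---|---|
| Arm effect at month 9 | 1.15-1.20 | 1.22-1.29 |
| Arm effect at month 18 | 1.12-1.28 | 1.17-1.40 |
| `β2` read at time zero (time uncentred) | 1.09-1.13 | 1.13-1.19 |
| `β4` (arm × time) | 1.000-1.003 | 1.000-1.004 |

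Setting the latent correlation to 1.0 in Step 2 gives 1.41-1.64. That would imply a correlation of 0.94-0.97 between 35-session bursts, above the protocol's 0.90, so I do not rely on it.

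**The case against.** The strongest reply is that the SAP already settles the matter. The introductory text, the burst numbering, Model 1 and the sentence after the equations all point to Burst 1, and only one subscript points elsewhere. Subscript 0 is also common shorthand for baseline, and the surrounding notation is careless: the Season coefficient is numbered 5 in Model 1 and 7 in Model 2. The run-in meaning is given in the imputation section, not for this model. All of this stands, and it is why I call the subscript a probable slip and not a chosen covariate. It does not make the printed equation right. The missing bar over `Y_i0` does not help either, because Model 1 also omits it.

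A reader might go further in three ways that the documents do not support.

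- **That Model 2 loses precision throughout, as if 24-29% of participants were lost.** Those figures (1 − 1/1.31 and 1 − 1/1.41) apply only to the arm effect at a single visit. The SAP singles out `β4` as summarising the treatment effect on change over time, and its standard error hardly moves.
- **That the check for random slopes could not be made.** The SAP does not say it will compare the likelihoods of Models 1 and 2; the likelihood ratio test it names here is for non-linear practice terms. The slope variance can be assessed within Model 2, or by refitting Model 2 without the slopes.
- **That the treatment estimate would be biased.** Both scores precede the intervention, and randomisation protects the comparison with either covariate.

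**Conclusion.** The inconsistency is real and sits in an operative equation, but its consequences are limited. If Model 2 were coded as printed, arm effects at a given visit would be estimated less precisely. At month 9 the standard error would be about 15-20% wider with a 10-session run-in, and roughly 13-29% across the other session counts tried. `β4` would change by less than 0.5%, provided within-person correlation across bursts is modelled.

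These sizes assume that the earlier study's reliabilities and the 0.90 correlation carry over, that session error is equal in the run-in and the bursts, and that the stratification covariates do not recover part of the loss. The loss of comparability between Models 1 and 2 needs none of these assumptions. The primary ANCOVA, which adjusts for the Burst 1 composite, is untouched. This is a minor correction.

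**What to change.** In the Model 2 equation, replace `Y_i0` with the Burst 1 average `Y_i1`, so that Models 1 and 2 differ only in their random effects. The cost is one subscript, with no effect on data collection or the primary analysis. If the run-in score was in fact intended, the SAP should say so and give the reason.

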the combinations present in the study array by pressing SAME or DIFFERENT buttons located at the bottom of the screen. Test array stimuli remained on the screen until response. Each trial had a 50% chance of being a SAME/DIFFERENT trial. Participants completed 6 trials per assessment (~45 seconds per assessment). The primary outcome for Color Shapes is corrected recognition rate (Hit-rate minus False-alarm rate).

The Shopping List task is a delayed recognition task where participants are asked to determine whether shopping list item-price combinations presented during a retrieval phase match the combinations judged during a price judgment phase of the task. The Shopping List task began with a price judgment phase where participants made subjective judgments of prices (in US dollars and cents) presented alongside hypothetical shopping list items (e.g. ‘bananas’). Participants made 10 subjective price judgments in total during the price judgment phase by pressing “YES” or “NO” buttons in response to the question “is this a good price for [shopping item]” (see Figure 3D). Price judgment phase stimuli were presented for 3000ms each, with an inter-stimulus interval of 1000ms between items. Immediately following the price judgment phase, the retrieval phase began, involving 10 forced-choice recognition trials. Each recognition trial presented one of the shopping list items judged during the price judgment phase accompanied by two prices. One price always matched the price judged during the price judgment phase. The other, non-target price values were always within 9USD of the correct, target price. Both prices were always below 10USD. The order of shopping list item tested during the retrieval phase was randomized with respect to the price judgment phase presentation order. Retrieval phase trials were presented until response. The Shopping List task lasted approximately 60 seconds per assessment. The primary outcome for Shopping List was proportion correct responses during the retrieval phase.

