Randomization occurs after the baseline visit and body measurements when participants are judged to be eligible to proceed to study activities. Stratified permuted block randomization with variable block sizes will be used to randomize participants to one of the two study arms in a 1:1 ratio. Randomization will be stratified on sex, age (<53 yr, 53-65 yr), and education level (no more than high school or equivalent, more than high school), for a total of 8 stratification factors.

Statistical Analysis Plan

Analysis of the Primary Outcome

The primary outcome is a global composite cognition score assessed at 9 months post baseline. The primary outcome will be calculated as a Z-score composite measure of three ambulatory cognitive tasks, each administered up to 35 times, during each measurement burst: Symbol Search, Grid Memory, and Color Shapes. For a given cognitive task (“domain”), an outcome score is calculated for each of up to 35 sessions which are administered over a 1-week measurement burst, approximately 5 sessions per day (administered throughout the day in 5 target ~2 hour windows). For each Burst, and each of the 3 domains, the assigned Z-score is derived from their burst-average response for that domain, and then the three domain burst-average Z-scores are averaged for that Burst to create the primary composite outcome. Note that the Symbol Search and Dot Memory Z-scores **must be multiplied by -1** before creating the composite score because lower scores are better for these tasks. Thus, an increase in the composite score represents better cognitive performance.

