Self-reported dietary outcomes indicative of the MHD diet include the DII score, which is derived from the self-reported data as both unadjusted and unadjusted for energy, water, and the following factors chosen because of hypothesized pro- or anti-inflammatory effects and because they were readily available summaries from the ASA24: total calories (KCAL), protein (PROT), total fat (TFAT), solid fats (SOLID_FATS), carbohydrates (CARB), total folate from food (FF), folate from non-food sources (non-FF), vitamin B12, carotenoids: retinol (RET), beta carotene (BCAR), alpha carotene (ACAR), cryptoxanthin (CRYP), lycopene (LYCO), Lutein+zeaxanthin (LZ); alpha tocopherol (ATOC), fatty acids (EPA, DPA, DHA), total fruits (F_TOTAL), green leafy vegetables (V_DRKGR), beans and peas (V_LEGUMES), whole grains (G_WHOLE), cured meats (PF_CUREDMEAT), poultry (PF_POULT), seafood high in n-3 fatty acids (PF_SEAFD_HI), nuts and seeds (PF_NUTSD), cheese (D_CHEESE), and added sugars (ADD_SUGARS).

Exploratory Analyses

Exploratory outcomes include the treatment effect on the two exploratory tasks (Shopping List and Rotation Span), which will be evaluated with similar longitudinal models developed for the three domains that make up the primary composite Z score (namely Models 1 and 2). Shopping List will be modeled with a linear mixed effects model. Due to the concern of departure in the Rotation Span scores from normality (a slight truncation), this domain will be modeled with generalized estimating equation with robust variance estimate.

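### Models 1 and 2 name no arm contrast at months 18 or 27; the one coefficient the SAP interprets is the change in the arm difference after month 9

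*SAP*

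**What the plan says.** SAP, Analysis of Secondary Outcomes, describes a "longitudinal session-level model with the post-baseline session level outcome", regressed on the baseline average, arm, time since baseline and session-level covariates. The burst definitions under Analysis of the Primary Outcome place Bursts 2 to 4 at months 9, 18 and 27. On the arm effect the SAP says: "The treatment effect in Models 1 and 2 will be modeled with a main effect an interaction with the continuous time variable". After the model equations it interprets one coefficient, beta_4, as the term that "summarizes the potential treatment effect on the change over time". Time of day is explicitly centred; no centring is stated for time since baseline.

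Color Shapes gets a similar GEE with a Poisson mean model for the count of incorrect responses. Under Exploratory Analyses, the only treatment analysis given for Shopping List and Rotation Span is one "which will be evaluated with similar longitudinal models developed for the three domains" of the composite.

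Visit-specific arm contrasts for cognition appear only at month 9: the primary ANCOVA on the composite, and a supportive analysis of "the treatment effect on the change from baseline at Burst 2 for each of the three individual task domain scores".

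**The concern.** The SAP Introduction counts durability and timing of effect among the important end-points, and uses them as a reason not to stop early. Protocol 1.1 (Aim A2) seeks the time course of benefit. Protocol 3 says the follow-up time points are there to establish a trajectory. Protocol 9.4 lists associations with the intervention over 27 months as exploratory outcomes. Protocol 9.2 expects that the arm difference may be greatest at month 9, so a benefit that is kept or that wanes is a shape the sponsor itself anticipates.

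A slope fitted only to post-baseline data is the wrong single number for those questions. It takes the same value, zero, for a fully sustained benefit as for no benefit. If the visit, contrast and test are left open, they will be chosen after the data are seen. The month-27 assessment, which falls after coaching ends at month 18, has no named arm contrast.

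**Working it through.** **Algebra.** Write D(t) for the arm difference at time t, given baseline and the other covariates. Models 1 and 2 give D(t) = beta_2 + beta_4*t, fitted to t = 0.75, 1.5 and 2.25 years. Hence beta_4 = dD/dt over months 9 to 27, and beta_2 = D(0), which lies outside the fitted range. The random slopes in Model 2 do not change the meaning of these fixed effects.

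**The plan's own figures.** Protocol 9.2 states 80% power for 0.35 SD with 125 per arm. At two-sided alpha 0.05 (assumed; no alpha is stated) I get 79%. The absolute difference is 0.35 x sqrt(2 x (1 - 0.90)) = 0.157, the stated 0.16. I use 0.16 only as a convenient size.

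**Coefficients for four shapes** (higher = better; arm difference at months 9/18/27). Signs reverse for raw Symbol Search and Grid Memory scores, "because lower scores are better for these tasks".

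| Shape | True difference | beta_2 | beta_4 per year |
|---|---|---|---|
| No benefit | 0/0/0 | 0 | 0 |
| Kept | 0.16/0.16/0.16 | 0.16 | 0 |
| Steady fade | 0.16/0.08/0 | 0.24 | -0.107 |
| Steady divergence from baseline | 0.053/0.107/0.16 | 0 | +0.071 |

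Fade: beta_4 = (0 - 0.16)/1.5 = -0.107, and beta_2 = 0.16 + 0.107 x 0.75 = 0.24, which is 1.5 times the largest effect at any visit. Divergence: beta_4 = 0.16/2.25 = 0.071, and beta_2 = 0 although month 27 stands at 0.16. These values do not depend on n, correlation or alpha.

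**Effect of the straight line.** Suppose the benefit holds to month 18 and then stops: 0.16/0.16/0. With equal weights the fitted month-18 value is the mean, 0.32/3 = 0.107. Generalised least squares with 125/119/113 per arm (n = 250 at month 9, then an assumed 5% loss per visit) gives 0.185/0.106/0.028 when all burst correlations equal 0.90. It gives 0.161/0.083/0.005 when 0.90 decays with lag. Against a true 0.16, month 18 is understated by a third to a half.

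**Precision** (SD 1, burst-level means, conditional on baseline). At exchangeable r = 0.90 the residual variance is 1 - 0.81 = 0.19 and the covariance is 0.90 - 0.81 = 0.09. Without dropout, the month-18 contrast from a burst factor has SE sqrt(2 x 0.19/125) = 0.055, and beta_4 has SE sqrt(2 x 0.10/(125 x 1.125)) = 0.038 per year. With dropout:

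| Quantity | SE, exchangeable 0.90 | SE, 0.90 decaying with lag |
|---|---|---|
| Month 18, burst factor | 0.056 | 0.075 |
| Month 18, linear time | 0.045 | 0.063 |
| beta_4 per year | 0.0391 | 0.0519 |

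At exchangeable 0.90, beta_2 has SE 0.073, against 0.055 to 0.057 for the burst-factor visit contrasts. It is therefore less precise than what it would stand in for.

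**The case against.** The strongest reply is that the SAP does not equate beta_4 with the whole treatment effect. It assigns that effect to a main effect and an interaction, and its description of beta_4 is a fair one for a slope interaction. This stands. A reader might infer that Models 1 and 2 would show no effect for a kept benefit. The documents do not support that: a kept 0.16 appears in full in beta_2, and every visit contrast can be computed from the fitted model. What is missing is the named combination.

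Second, beta_4 answers a real question. Protocol 9.1 expects stability in one arm and decline in the other, and steady divergence gives beta_4 the sign of benefit. That also stands. A near-zero beta_4 beside a positive month-9 task result would be informative if precise. Its 95% half-width over 18 months is 1.96 x 1.5 x 0.0391 = 0.115 at exchangeable r = 0.90, which would exclude complete loss of a 0.16 benefit. At r = 0.50 (SE 0.0871) it is 0.256, which would not. The SAP does not plan that joint reading, and the two exploratory tasks have no month-9 result to set beside it.

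Third, these analyses are secondary or exploratory, and the 0.16 is a difference in the global score, whereas Models 1 and 2 analyse single tasks. Both are true. They limit the weight of the precision figures but leave the algebra untouched.

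Fourth, for Color Shapes the algebra holds on the ratio scale only. With a log link (assumed), zero interaction means a constant rate ratio. A constant absolute difference can give a non-zero interaction if the comparison arm's error rate drifts.

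**Conclusion.** The point holds as a gap in prespecification. The one coefficient that the SAP interprets in Models 1 and 2 cannot separate a sustained benefit from none, and the accompanying main effect is an extrapolation to month 0. No arm contrast is named at months 18 or 27 for the three primary tasks, nor at any visit for Shopping List and Rotation Span.

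It should be fixed, but it does not threaten the main result. The primary ANCOVA and the month-9 task analyses are unaffected, and beta_4 remains a valid measure of divergence or waning after month 9. The coefficient values follow from the model as written, with time uncentred. The standard errors and the smoothed month-18 values rest on assumed correlations, SD 1, assumed dropout and burst-level means. They are illustrative only, because the documents give no single-task difference.

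**What to change.** In Models 1 and 2 and the corresponding GEE models, including those for Shopping List and Rotation Span:

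- Prespecify beta_2 + beta_4*t at months 9, 18 and 27, with confidence intervals, as the reported treatment effects. For the Color Shapes Poisson model, report rate ratios and state the link.
- Describe beta_4 as the change in the arm difference after month 9.
- Add, as a sensitivity analysis, a fit with arm by burst as a three-level factor, because the linear month-18 value is smoothed.

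The cost is a few lines of SAP text and modest code, with no new data. The burst-factor fit is less precise at month 18 (SE about 0.056 against 0.045 at exchangeable r = 0.90). It also pools the spread in Burst 2 timing that the visit window allows, unless a timing covariate is added. Those are reasons to keep linear time as the main fit and the factor as the check.
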